5.4 Dose delays, modifications or discontinuation for hematologic side effects

5.4.1 Thrombosis/Embolism: Subjects who experience a deep venous thrombosis or a pulmonary embolus, a TIA or stroke, or a myocardial infarction at any time while on eltrombopag will discontinue the drug and go off study. Patients with platelet counts of > 50,000/uL at the time of thrombosis will be treated with enoxaparin or another appropriate anticoagulant as clinically indicated until the platelet count drops below 20,000/uL with discontinuation of eltrombopag. They will be treated for the thrombotic event as otherwise clinically-indicated.

5.4.2 Evidence for disease progression: The presence of persistent morphologic abnormalities (red cell teardrop forms; immature blast cells) or the development of significant worsening of anemia (requiring transfusions) or neutropenia while on study will require discontinuation of eltrombopag and performance of a bone marrow examination to assess for development of abnormal fibrosis or progression to MDS or AML.

Any morphological changes in the bone marrow fulfilling current WHO criteria for MDS or cytogenetic abnormalities indicating clonal hematopoiesis will require discontinuation of eltrombopag.

5.4.3 Thrombocytosis or erythrocytosis: Patients will have eltrombopag discontinued for one week if platelets increase to >400,000/uL or Hb to > 16 gr/dL, and if counts have fallen below these cutoffs, drug can be restarted at 50% dosage.

5.5 Extended access to study drug

Subjects with improvement in blood counts or transfusion requirements but not yet meeting response criteria at 16 weeks may continue study medication for an additional 4 weeks (to ensure eligibility) prior to being consented for entry into the extended access part of the trial. Subjects that have their response assessment extended an additional 4 weeks and have a response will be able to go on the extended access part of the trial after signing the consent. Per dosing criteria given in section 5.2, patients may remain on the extended access as long as they maintain a treatment response.

Dose adjustments during extended access: Eltrombopag will be discontinued in patients that reach robust hematologic response (platelets >50,000/ μ L and Hb > 10 g/dL in the absence of transfusions, and neutrophils > 1,000) for more than 8 weeks. In patients who maintain initial response criteria (but do not meet robust response criteria in all three lineages) and show no further clinically-significant improvement in their counts over a 6 month period eltrombopag can be stopped at PI's discretion. Eltrombopag can be re-initiated at PI's discretion if peripheral cell counts drop below numbers measured when the patient entered the study or if platelets drop to <30,000/ μ L, Hb to <9g/dL, or ANC to <500/ μ L. Once count stabilization again occurs, a slow dose reduction by 50 mg increments can be performed to identify the lowest dose necessary to keep counts over these thresholds.

5.6 Permitted Supportive care

- Transfusional supportive care (e.g., blood and platelets) as clinically indicated. Estrogens or combination OCPs as indicated for uterine bleeding
- Prophylactic antibiotics and antivirals as clinically indicated
- The PI should be informed about all medication changes

5.7. Non-permitted medication

Romiplostim (N-Plate) or IL-11 (Neumega) should not be administered.

5.8 Concurrent Medications:

Rosuvastatin: In vitro studies demonstrated that eltrombopag is not a substrate for the organic anion transporter polypeptide, OATP1B1, but is an inhibitor of this transporter in vitro and as evidenced by increased plasma rosuvastatin levels when eltrombopag and rosuvastatin were co-administered in a clinical drug interaction study. When co-administered with eltrombopag, a reduced dose of rosuvastatin should be considered and careful monitoring should be undertaken. In clinical trials with eltrombopag, a dose reduction of rosuvastatin by 50% was recommended for co-administration of rosuvastatin and eltrombopag. Concomitant administration of eltrombopag and other OATP1B1 substrates should be undertaken with caution.

Inhibitors of Cytochrome p450: In vitro studies demonstrate that CYP1A2 and CYP2C8 are involved in the oxidative metabolism of eltrombopag. Trimethoprim, gemfibrozil, ciprofloxacin, fluvoxamine and other moderate or strong inhibitors of CYPs may therefore theoretically result enhanced activity of eltrombopag, however these interactions have not yet been established in clinical studies. Patients on cyclosporine requiring prophylaxis against PCP should be given inhaled pentamidine instead of TMP/SULF. NIH SAA patients are routinely placed on pentamidine instead of TMP/SULF for PCP prophylaxis to avoid potential marrow-suppressive effects of TMP/SULF anyway. Other CYP inhibitors can be used concomitantly but with careful attention to possible increased eltrombopag activity and toxicity.

Other medications: Patients may continue on any dietary supplements or medications that they were prescribed prior to study enrollment for co-morbid conditions, and standard anti-infectious prophylaxis medications including pentamidine, valacyclovir, and voriconazole.

5.9 Instructions to patients

Timing in relation to food: Patients will be advised to take eltrombopag on an empty stomach (1 hour before or 2 hours after a meal)

Timing in relation to antacids: Because co-administration of eltrombopag with antacids decreased plasma AUC of eltrombopag by 70%, patients will be advised to take the eltrombopag at least 4 hours apart from antacids and other products containing polyvalent cations (i.e. aluminum, calcium, magnesium, iron, selenium and zinc) such as mineral supplements and dairy products.

Vigorous activities: You should avoid vigorous activities, as mild trauma could result in bleeding.

6.0 CLINICAL MONITORING

6.1 Pre-study Evaluation

Baseline status will be evaluated as follows:

- Medical History and physical examination
- Concurrent medication review
- Baseline assessments (done at screening or diagnostic workup, not repeated on study)
 - Folate level
 - B12 level
 - Iron panel (ferritin, transferrin, % saturation)
- Baseline laboratory studies (evaluations designated with an * must be done within 7 days of the first dose of study drug, all others should be within 6 months of study entry or as indicated)
 - Complete blood count with differential*
 - Reticulocyte count*
 - Chem 20 panel (Acute care (Na, K, Cl, CO₂, Creatinine, Glucose, and Urea Nitrogen), Mineral (Phosphorus, Magnesium, Albumin, and Calcium), Hepatic (Alk Phosphatase, ALT, AST, Total Bilirubin, and Direct Bilirubin), and Other (Total Protein, CK, Uric Acid, and LDH) panel)*
 - Pregnancy test (urine or blood HCG in women of child bearing potential)*
 - Coagulation screens (PT, PTT) (within 12 weeks prior to consent).
 - Thyroid function tests (within 12 weeks prior to consent).
 - Peripheral blood smear (at baseline and at response evaluation)
 - Viral serologies for HIV, hepatitis B, C, HSV, EBV and CMV (within 12 weeks prior to consent).
 - HLA typing (if not already available) (within 12 weeks prior to consent).
 - DAT (direct antiglobulin test) (within 12 weeks prior to consent).
 - Flow cytometry of the peripheral blood for GPI-cells (within 12 weeks prior to consent).
- 24 hour urine collection to determine the total iron content at PI's discretion if indicated for iron metabolism and excretion studies
- Iron panel (ferritin, transferrin, % saturation) at PI's discretion if indicated for iron metabolism and excretion studies
- Bone marrow aspirate and biopsy with reticulin and collagen fiber staining and cytogenetic analysis (morphology, cellularity, percentage of blast cells, and/or chromosomal analysis) within 12 weeks of first dose of study drug
- FACT questionnaire within 7 days prior to start of first dose of study drug

6.2 Monitoring study drug initiation through primary endpoint (response assessment at week 16 or week 20 +/- 7 days)

Subjects will be monitored so long as they remain on study drug through week 16 or week 20. Subjects may be followed by their home physician or at the Clinical Center. Progress notes and lab tests not done at the NIH will be faxed to the Research Nurse. Subjects will be evaluated for response at week 16 (+/- 7 days) and week 20 (+/- 7 days) if needed at the clinical center. Evaluations designated by the “***” below will only need to be completed for subjects at response assessment either at week 16 or 20. At the clinical investigator's discretion, participants may be evaluated more frequently if medically indicated based on disease status. Subjects must have interim weekly blood tests drawn by their referring health care provider or at the NIH. Women of childbearing potential will also have pregnancy tests by their referring health care provider or at the NIH at the time points listed below. If subjects are to be followed at home, progress notes (if available) and laboratory results from their health care provider and laboratory must be faxed to the study research nurse and if this requirement is not fulfilled strictly subjects will be taken off study. Subjects may have the testing performed at the NIH. The following assessments will be done:

During 16 or 20 weeks (+/- 7 days) landmark visits

- Clinical assessment and vital signs
- Medication review with attention to compliance with eltrombopag so that early discontinuation and subsequent rebound exacerbation is carefully monitored CBC with differential
- Acute care (Na, K, Cl, CO₂, Creatinine, Glucose, and Urea Nitrogen), Mineral (Phosphorus, Magnesium, Albumin, and Calcium), Hepatic (Alk Phosphatase, ALT, AST, Total Bilirubin, and Direct Bilirubin), and Other (Total Protein, CK, Uric Acid, and LDH) panel
- Coagulation screens (PT, PTT)**
- DAT (direct antiglobulin test) (as clinically indicated)
- Type and screen (as clinically indicated)
- Pregnancy test (urine or blood HCG in women of child bearing potential) (after 16, 20** weeks of medication (+/- 7 days))
- Flow cytometry of the peripheral blood for GPI-cells**(+/- 3 weeks)
- Bone marrow aspirate and biopsy with reticulin and collagen fiber staining and cytogenetic analysis at primary end point (morphology, cellularity, percentage of blast cells, and/or chromosomal analysis by PCR)** (+/- 3 weeks)
- FACT questionnaire ** (+/- 3weeks)
- 24 hour urine collection to determine the total iron content at PI's discretion if indicated for iron metabolism and excretion studies
- Iron panel (ferritin, transferrin, % saturation) at PI's discretion if indicated for iron metabolism and excretion studies
- In pediatric patients and selected adult patients blood for pharmacokinetic evaluation of eltrombopag levels with samples drawn pre-dose, and at 2,4,6, and 8 hours after the dose, with an optional final sample at 24 hours after the first dose.

On Study Monitoring (through 16 and 20 weeks +/- 5 days)

Subjects may be followed by their home physician or at the Clinical Center. Progress notes and lab tests not done at the NIH will be faxed to the Research Nurse. The PI will review outside test results and these will be uploaded into CRIS and filed in the research charts, and all lab data will be recorded.

- Complete blood counts with differential (every 2 weeks +/-5 days)
- ALT, AST, Total Bilirubin or Direct Bilirubin,(every two weeks +/- 5 days)

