
Starting dose will be 150 mg/day (75 mg/day in East Asian). The dose will be increased by 50 mg/day (25 mg/day Asian) every 4 weeks until subjects reach the maximum dose of 300 mg/day (150mg/day Asian). This will allow reaching the 300 mg dosing at the same time as the previous cohort and generates the least changes in the treatment schema. The rationale for using the half dose for East Asian patients is unchanged; the change in the starting Eltrombopag dose is based on our growing experience with dosing Eltrombopag in bone marrow failure patients (no hematologic response seen at doses lower than 150 mg/day and all patients were increased at least up to 200 mg/day without any side effects) for patients with bone marrow failure syndromes, as well as the recommendation from our DSMB reviewers in 2014. Also, the extended time for each dose, from 2 to 4 weeks will allow for better identification of patients that respond at lower doses than the maximal 300 mg/day.

Pediatric dosing:

For pediatric subjects, there is a predicted higher weight-adjusted drug clearance than older children and adults based upon studies of several drugs approved for use in children, such as anticonvulsants, proton pump inhibitors, theophylline, and HIV protease inhibitors, have routinely demonstrated that young children have higher weight-adjusted drug clearance than older children and adults [Lamictal Package Insert, 2007; Trileptal Package Insert, 2007; Keppra Package Insert, 2008; Prilosec Package Insert, 2008; Kaletra Package Insert, 2007; Viracept Package Insert, 2007; Grygiel, 1983]. The recently published results of a phase II pediatric chronic ITP study (PETIT), subjects between 1 and 5 years received a maximal mean dose of 2.9 mg/kg eltrombopag once daily, while subjects between 6 and 17 years of age received an average daily dose of 57.3 mg daily (13). The maximum dose used in the PETIT trial among all age groups is 75 mg daily dose. In the dose finding part of the study 5 patients was recruited to cohort 3 (ages 1 to 5 years). These subjects initiated dosing with 0.7 mg/kg once daily and increased to at least 1.4 mg/kg once daily by the Week 12 visit. Patients in this cohort received a median of 66mg eltrombopag daily (3mg/kg: range 34-75mg). Preliminary PK data collected for 3 subjects (ages ranging from 2 to 5 years) receiving eltrombopag 1.1 to 1.2 mg/kg once daily at Week 6 suggest that this regimen delivers

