4.2 Exclusion criteria

- 4.2.1 Known Diagnosis of Fanconi anemia
- 4.2.2 Counts that meet criteria for severe aplastic anemia
- 4.2.3 Infection not adequately responding to appropriate therapy
- 4.2.4 HIV positivity
- 4.2.5 Creatinine > 2.5 mg/ dL
- 4.2.6 Bilirubin > 2.0 mg/ dL, including congenital abnormalities in the bilirubin count
- 4.2.7 SGOT or SGPT > 5 times the upper limit of normal
- 4.2.8 Hypersensitivity to eltrombopag or its components
- 4.2.9 Female subjects who are nursing or pregnant or are unwilling to take oral contraceptives or refrain from pregnancy if of childbearing potential
- 4.2.10 Evidence of an active malignant hematological or clonal disorder, or abnormal cytogenetic studies of the bone marrow performed within 12 weeks of study entry
- 4.2.11 Unable to understand the investigational nature of the study or give informed consent and does not have a legally authorized representative or surrogate that can provide informed consent per section 10.5
- 4.2.12 Moribund status or concurrent hepatic, renal, cardiac, neurologic, pulmonary, infectious, or metabolic disease of such severity that it would preclude the patient's ability to tolerate protocol therapy, or that death within 7-10 days is likely
- 4.2.13 Treatment with horse or rabbit ATG or Campath within 6 months of study entry
- 4.2.14 Treatment with cytokines such as G-CSF or Erythropoietin
- 4.2.15 Subjects with known liver cirrhosis in severity that would preclude tolerability of eltrombopag as evidenced by albumin $< 35\text{g/L}$
- 4.2.16 Life expectancy of less than 3 months
- 4.2.17 Patients with an active diagnosis of cancer who have received chemotherapeutic treatment or other specific antineoplastic drugs or radiation therapy within 6 months of study entry
- 4.2.18 Unable to take investigational drug

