10.0 HUMAN SUBJECT PROTECTION

10.1 Rationale for Subject Selection

The study will be open to all subjects who satisfy the inclusion criteria and provide an informed consent to the protocol. No subjects will be excluded from participation based on gender, race or ethnicity.

Epidemiologic studies suggest that an estimated 2-4 million cases of aplastic anemia will be diagnosed each year worldwide; the incidence occurs in three peaks: 2-5 years, 20-25 years and 55-60 years; cases are approximately evenly split between male and females. Based on previous experience at our institution, approximately 60 new patients with aplastic anemia per year will be evaluated for protocol participation and the distribution in this patient population will be:

Gender: 60% males and 40% females;

Race/ethnicity: approximately 55% White, 15% Black, 6% Asian and 24% Hispanic;

Age: will range between 2 and 82 (median age of 30) and that 15% of patients will be under the age of 18.

For subjects of Asian heritage: Plasma eltrombopag exposure was approximately 70% higher in East Asian (i.e. Japanese, Chinese, Taiwanese and Korean) subjects as compared to non-East Asian subjects who were predominantly Caucasian. Therefore, subjects of Asian heritage will be included but they will be initiated at a lowered dose and monitored closely.

For subjects with renal impairment: The pharmacokinetics of eltrombopag has been studied after administration of eltrombopag to adult patients with renal impairment. Following administration of a single 50 mg dose, there was a trend for reduced plasma eltrombopag exposure in patients with renal impairment, but there was substantial variability and significant overlap in exposures between patients with renal impairment and healthy volunteers. Therefore, patients with impaired renal function will be included but participation will be monitored closely.

For subjects with hepatic impairment: The pharmacokinetics of eltrombopag has been studied after administration of eltrombopag to adult patients with hepatic impairment. Following the administration of a single 50 mg dose, the AUC_{0-∞} of eltrombopag was increased by 41% in subjects with mild hepatic impairment and by 80% to 90% in subjects with moderate or severe hepatic impairment compared with

healthy volunteers. Therefore, patients with minimally impaired hepatic function will be included but participation will be monitored closely.

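### While subjects take eltrombopag, creatinine is named only every 6 months on extended access, and before that only at baseline and week 16 or 20, although two-weekly draws already exist

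*Combined protocol and SAP*

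**What the plan says.** **Entry.** Section 4.2.5 excludes "Creatinine > 2.5 mg/ dL", so a subject at or below that value may enter. Section 10.1 adds that "patients with impaired renal function will be included but participation will be monitored closely". The reason it gives is pharmacokinetic: "there was a trend for reduced plasma eltrombopag exposure in patients with renal impairment", with wide variability.

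**Dose.** Under the schedule in force since January 2015 (section 2.6), adults start at 150 mg/day (75 mg/day if East Asian). "The dose will be increased by 50 mg/day (25 mg/day Asian) every 4 weeks until subjects reach the maximum dose of 300 mg/day"; for East Asian adults the ceiling is 150 mg/day. Children receive a fixed dose.

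**Laboratory schedule.** Creatinine belongs to the acute care panel. Section 6.1 includes that panel among the baseline tests that "must be done within 7 days of the first dose of study drug". It is next named at the week 16 visit, and at week 20 for those who continue (6.2). It is then named every 6 months on drug (6.3) and at the optional visit 6 months after stopping (6.4). The two-weekly draws between those points list blood counts and "ALT, AST, Total Bilirubin or Direct Bilirubin,(every two weeks +/- 5 days" in 6.2. The equivalent list in 6.3 adds a reticulocyte count. Appendix B agrees: the acute care row is blank at weeks 2 to 14, at week 18, and in the two-weekly extended-access column.

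**Tests with unnamed content.** Section 6.2 also states: "Subjects must have interim weekly blood tests drawn by their referring health care provider or at the NIH". It does not itemise them. Section 8.6.2 has laboratory tests continuing to 30 days off drug, again without a list.

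**The concern.** The CTCAE toxicity profile is part of the primary endpoint (8.2). Section 9.2.2 collects a laboratory abnormality when it progresses to grade 3 or 4, has clinical consequences or is judged clinically important. It can do so only if the analyte is drawn. With creatinine named this rarely, a grade 3 or 4 or clinically important renal event could be found late, or its onset misdated.

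The protocol's own evidence gives some reason to look more often, and more so with longer exposure:

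- Section 2.4.4 reports proximal tubular toxicity in the 2-year mouse study at 1.4-fold the clinical exposure in ITP, and describes the effect as time-dependent. Extended access is the long-exposure phase, and it has the longest gap.
- Section 10.3.1 lists thrombotic microangiopathy with acute renal failure as a rare post-marketing event. Low counts are expected in this disease and are not recorded as adverse events (9.2.2), so the two-weekly blood count is a weak substitute for a renal test.
- The reassurance in 2.4.6 about short-term use comes from 6-week studies at 30 to 75 mg. Section 2.6 says "all patients were increased at least up to 200 mg/day without any side effects", but does not address renal function at 300 mg.

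**Working it through.** No power or error-rate calculation is involved, and the plan states no figure to reproduce. The check compares the schedules and then does calendar arithmetic.

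**Step 1. What is named when (6.1 to 6.4, Appendix B).**

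| Time point | Counts | Liver tests | Creatinine |
|---|---|---|---|
| Baseline | yes | yes | yes |
| Weeks 2, 4, 6, 8, 10, 12, 14 | yes | yes | no |
| Week 16 (and week 20 if continued) | yes | yes | yes |
| Week 18 | yes | yes | no |
| Extended access on drug, two-weekly | yes | yes | no |
| Extended access on drug, 6-monthly | yes | yes | yes |
| Optional visit 6 months after last dose (6.4) | yes | yes | yes |

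Through week 16 this gives 8 on-treatment liver assessments and 1 creatinine.

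**Step 2. Gap on extended access.** Taking 6 months as 26 weeks, the nominal gap is 26 × 7 = 182 days. With one visit 30 days early and the next 30 days late, it is 182 + 30 + 30 = 242 days.

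**Step 3. Gap in the initial phase.** From first dose to week 16 is 16 × 7 = 112 days. If the baseline panel is drawn 7 days before the first dose and the week 16 visit falls 7 days late, the gap is 7 + 112 + 7 = 126 days. This uses the first-dose anchor in 6.1; Appendix B ties the same baseline tests to consent instead.

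**Step 4. Dose over that interval, for an adult escalated at every step.**

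| Nominal day | Non-East Asian | East Asian |
|---|---|---|
| 0 | 150 mg | 75 mg |
| 28 | 200 mg | 100 mg |
| 56 | 250 mg | 125 mg |
| 84 | 300 mg | 150 mg |

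All three increases come before the first named on-treatment creatinine, which falls 112 − 84 = 28 days after the maximum is reached. A subject who stops before week 16 has no named on-treatment creatinine.

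**Step 5. With creatinine on the existing draws.** The nominal gap is 14 days in both phases. The initial-phase maximum is 7 + 14 + 5 = 26 days (baseline to week 2) or 5 + 14 + 7 = 26 days (week 14 to 16). The extended-access maximum is 7 + 14 + 7 = 28 days.

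**Step 6. Extra results.** Weeks 2 to 14 add 7, and week 18 makes 8. On extended access, 182 / 14 = 13 draws, less the 1 already covered by the 6-monthly panel, adds 12 per 6 months.

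**The case against.** The case for leaving the schedule alone is substantial.

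- **Animal data.** Section 2.4.4 reports no renal toxicity in mice at 13 weeks, at higher exposure than the lowest dose of the 2-year study. Rats at 28 weeks and dogs at 52 weeks were also clear, at up to 4.5- and 2.9-fold ITP exposure. This weakens the argument for the 16-week phase in particular.
- **Closest clinical population.** In 43 patients with severe aplastic anemia (10.3.1), 11 were treated beyond 6 months and 7 beyond a year. No renal term appears among the adverse reactions, though that table lists only those at 10% or more.
- **Other exposure.** The long-term ITP studies are said to confirm the earlier safety profile (2.4.6). Median treatment in the extension study was 194 days, at a median dose of 50 mg (2.8).
- **Other routes to detection.** The weekly bloods may include creatinine. More frequent evaluation is allowed if medically indicated (6.2). Unscheduled results sent in are reviewed, with grade 3 or 4 findings entered in the database (9.2.2). A subject stopped for a listed adverse event is followed until it resolves (8.6.2).
- **Label.** The label text quoted in 10.3.1 asks for hepatic and ocular monitoring and sets no renal schedule.

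All of this stands, and it limits the weight of the point. It does not close the gap: none of the other routes requires a creatinine, and none of the clinical data cited speaks to renal function at the highest doses.

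A reader might infer more than the documents support:

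- *That creatinine is never measured between visits.* It is not named; it may be drawn.
- *That the schedule breaks a promise in 10.1.* The reason given there is drug exposure, so it is not an undertaking to watch for nephrotoxicity. It does single these subjects out for close monitoring without a matching test.
- *That raised entry creatinine increases drug-related renal risk.* The documents do not show this: the exposure trend is downward, and unchanged drug is not detectable in urine (2.4.5).
- *That silent low-grade rises are being lost.* Section 9.2.2 does not set out to collect them.

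**Conclusion.** The point holds as an inexpensive improvement to safety monitoring. On drug, the named creatinine interval is nominally 182 days on extended access (at most about 242) and 112 days in the initial phase (at most 126), against 14 days for liver tests.

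The case is stronger on extended access, where exposure is long and the only animal renal signal depends on time. In the initial phase it rests on a lack of stated renal data at the top doses and on one rare event.

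The conclusion assumes that blood tests with unlisted content do not reliably include creatinine. If they do in practice, the change only documents what already happens. The number of subjects with raised baseline creatinine is not given, so no count of those affected can be offered. No effect on the response analysis is claimed.

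**What to change.** 1. In section 6.3 and the two-weekly extended-access column of Appendix B, add creatinine to the existing draw.
2. Do the same in section 6.2 and Appendix B for weeks 2 to 14 and week 18, at minimum for subjects with raised baseline creatinine.
3. In section 8.6.2, name creatinine among the laboratory tests taken at early discontinuation.

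The cost is one analyte on a sample already being taken, with no added visit or procedure. That means 7 or 8 more results per subject in the initial phase and about 12 per 6 months on extended access, all of which must be reviewed and graded. If enrolment has ended, the first item matters most, because it reaches everyone still on drug.
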